##### **Study overview**

Participants will be up to 380 (including up to 80 intermittent [ITS]) non-treatment-seeking adult smokers who are not regular e-cig users. Participants will smoke their usual brand (UB) during Phase 1 (Baseline; week 1) and will exclusively smoke the VLNCC during Phase 2 (weeks 2-4). During phases 3 (weeks 5-7) & 4 (weeks 8-10), smokers will be instructed to freely use any combination of assigned VLNCC and e-cigs (VLNCC+ECIG). All subjects will receive both e-cig doses (ECIG-Hi [36 mg/ml] and ECIG-Lo [8 mg/ml]) with order counter balanced across phases 3 and 4. At least 80 daily smokers will be randomized to the JUUL condition (VLNCC for phase 2 and combined VLNCC+JUUL-Hi or -Lo for phases 3 & 4). All participants in the JUUL group will receive both e-cig doses (JUUL-Hi [JUUL 5%; 59 mg/ml nicotine] and JUUL-Lo [JUUL 3%; 35 mg/ml nicotine]), with order counter-balanced across phases 3 and 4.

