**Lack of a cessation endpoint.** If we could, we would be submitting protocols to evaluate electronic cigarettes as a potential smoking cessation aid, because anecdotal evidence suggests that smokers are already doing so. Unfortunately, we are not yet able to evaluate electronic cigarettes as a smoking cessation therapy in the U.S. Smoking cessation is considered a medical indication and products making a medical claim are overseen by CDER, which is a separate and independent component of the FDA from CTP, which oversees tobacco and nicotine regulation. Unlike the pharmaceutical industry, no electronic cigarette manufacturers have taken the necessary steps to assemble a master file needed for obtaining an investigational new drug (IND) application, which must be granted before cessation with electronic cigarettes could be studied. Researchers in the US have been complaining about this conundrum for years but it is not something we can control and in fact we cannot have cessation as an endpoint in any of our studies (except for naturalistic quitting). Moreover, because the focus is on harm reduction, we only select smokers who are not presently interested in quitting for our electronic cigarette studies for ethical reasons.

**Duration of product exposure.** While a one week usual brand smoking is typical for establishing a base rate in most observational studies, the length of the VLNC and each VLNCC+ECIG dose condition (3 weeks each) could be insufficient to determine stable responding. However, in our preliminary studies we observed little change in CPD for VLNCCs beyond week 3. There is no data to estimate length of exposure to e-cigs needed to establish stable responding, but we feel 3 weeks is sufficient since individuals in the high dose condition will receive levels of plasma nicotine comparable to combustible cigarettes within as little as 10 puffs, and this will provide the intended contrast to the lower plasma nicotine levels of the low dose e-cig within the same time frame.

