## E. PROTECTION OF HUMAN SUBJECTS

### Human Subjects Involvement, Characteristics and Design

Volunteers recruited for this study (N= up to 380) will be current smokers from the state of Texas area and/or Houston metropolitan community, who respond to media announcements related to the study (see Appendix AA). The Tobacco Research and Treatment Program's web screener database for tobacco users, outlined in IRB-approved PA18-0423, also may be used as a recruitment source for this study. This database houses data collected from an internet-based screening questionnaire to recruit tobacco users from the Houston area, as well as across Texas more broadly, who may be interested in participating in tobacco use and cessation studies at MD Anderson Cancer Center. PA18-0423 allows the sharing of data with IRB approved MD Anderson protocols. The Houston population is estimated at over 4 million with an ethnic distribution of 59% Caucasian, 19% African-American, 5% Asian, and 0.4% Native American, with 33% Hispanic or Latino (of any race) [157].

As shown in **Table 3**, inclusion criteria will include signing consent and agreeing to all study procedures, being between the ages of 21 and 65, having a working telephone and address where they may be reached, being interested in trying novel nicotine products, able to follow verbal and written instructions in English, and be the only participant in their household. Individuals will be excluded if they are unwilling to refrain from other e-cigarette use for the duration of the study, other than what is provided to them for study purposes, have had a bronchial or respiratory infection within the past 14 days, a spirometry FEV1 percentage reading is <50 (severe to very severe), have unstable medical conditions as determined by the medical team, abnormal heart rhythms or cardiovascular disease (stroke, chest pain, heart attack) in the last 3 months, meets criteria for Major Depressive Syndrome or suicidality on the PHQ-9, self-report of past or current diagnosis of bipolar disorder or schizophrenia/schizoaffective disorder, report use of tobacco products other than cigarettes or little cigars on 10 or more days in the last month, report recent (past 90 days), current, or planned (within the next 45 days) involvement in smoking cessation activities, or have a positive urine pregnancy test at screening.

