**Exclusion Criteria:**

- Unwilling to refrain from other e-cigarette use for the duration of the study, other than what is provided to them for study purposes.
- Current/recent use of certain medications:
  - a. Smoking cessation meds (past 90 days; e.g., Wellbutrin, Bupropion, Zyban, NRT, Chantix)
  - b. Certain medications to treat depression (last 14 days; e.g., Amitriptyline)
  - c. A case by case determination will be made by study physician for medication on the precautionary list (e.g., nitroglycerin)
  - d. self-reported daily use of opioids for 30 days or more on phone screen or at screening is exclusionary however PRN use is allowed (e.g., 3 to 7 days per week or less or if more frequent, use less than a month's duration.)
- Unstable medical condition as determined by the medical team
- Self-reported bronchial or respiratory infection in the last 14 days (this criterion waived during COVID-19 pandemic)
- Subject's spirometry FEV1 percentage reading is  $<50$  (severe to very severe obstruction) (this criterion waived during COVID-19 pandemic)
- Self-reported abnormal heart rhythms or cardiovascular disease (stroke, chest pain, heart attack) in the last 3 months
- Meets criteria for Major Depressive Syndrome or suicidality on the PHQ-9
- Self report of past or current diagnosis of bi-polar disorder or schizophrenia/ schizoaffective disorder
- Self-reported other tobacco use besides cigarettes or little cigars (e.g., hookah, cigarillos, smokeless tobacco, chewing tobacco, pipes, cigars, etc.) on 10 or more days in the last month.
- Recent (past 90 days), current, or planned (within the next 45 days) involvement in smoking cessation activities
- Positive urine pregnancy test at screening. Women who are one year post-menopausal, or who have had a tubal ligation or a partial or full hysterectomy will not be subject to a urine pregnancy test.
- Women that are breastfeeding or of childbearing potential and not protected by a medically acceptable, effective method of birth control while enrolled in the study. Medically acceptable contraceptives include: (1) approved hormonal contraceptives (such as birth control pills, patches, implants or injections), (2) barrier methods (such as condom or diaphragm) used with a spermicide, or (3) an intrauterine device (IUD). Contraceptives sold for emergency use after unprotected sex are not acceptable methods for routine use

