#### ***Baseline Screening.***

Participants will not be randomized into the study until Visit 1. Participants who remain eligible after the baseline screening visit will be scheduled to return for Phase 1 as soon as the following week after the baseline visit. Participants will be registered in the institutional database (CORe) within 2 business days of signing consent.

At the baseline screening (Visit 0), which will occur within 30 days of the telephone screen, study participants will be asked to provide medical/surgical history (see Appendices E & QQ), smoking history (see Appendix H) and to complete other assessments as shown in Table 4. Additionally, participants will be asked to fill out two forms related to additional contacts should we no longer be able to reach them (see Appendix C). They may also be provided a staff contacts list and an appointment card if eligible during the visit (see Appendices L and NN). Current and past medical history will be collected. These items will be given to a licensed medical professional, such as a research nurse, physician's assistant, or MD, to review eligibility. In some cases, the medical team may request clearance for participation be signed off by the participant's medical provider (see Appendix TT) prior to enrollment.

Participants unable to complete the Baseline screening visit within 30 days of the initial telephone assessment will be allowed to undergo a second telephone assessment and given an additional 30 days to complete the Baseline screening visit. If they do not complete the Baseline by this time point, they will no longer be considered eligible for study participation and must undergo a 90-day waiting period to re-enroll.

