**Table 4. Study Time Line and Procedures.**

Study Timeframe	Table 4. Study Time Line and Procedures								
	Baseline Screening	Phase 1 Wk 1 (Randomization Visit)	Check -Up Call #1	Phase 2 Wk 2-4	Check-Up Call #2	Phase 3 Wks 5-7	Phase 4 Wks 8-10	30 Day Follow Up Call	
Visit #	0	1		2		3	4	FU Call	
Study Day	-29	1	8	11*	29	32*	50	71	101
ASSESSMENTS									
Phone Screen (Basic Eligibility)	X								
Informed Consent Signed	X								
Pregnancy Test	X	X		X		X	X		
Expired CO†	X	X		X		X	X		
Height	X								
Weight	X	X		X		X	X		
Urine- Compliance (cotinine, TNE, & MA)			X			X		X	
Formaldehyde DNA			X		X		X	X	
Spirometry lung function test†	X							X	
PHQ-9 & GAD-7	X								
Demographics & Smoking History	X								
Medical History	X								
Concomitant Meds	X	X		X		X	X		
Health Changes Questionnaire		X		X		X	X		
Adverse Events		X		X		X	X		
EMA Random Assessments**						X		X	
EMA Daily Diary**					X		X	X	
Product Accountability			X		X		X	X	
TLFB	X	X		X		X	X	X	
ASI-3	X								
CES-D	X								
Mood History	X								
K-6	X								
FTND	X								
MNWS	X	X		X		X		X	
QSU - Brief	X	X		X		X		X	
PANAS	X	X		X		X		X	
American Thoracic Society questionnaire (ATSQ)	X	X		X		X		X	
Purchase Tasks – Usual Brand		X		X		X		X	
Purchase Tasks – Study Cigarette				X		X		X	
Purchase Tasks – E-Cigarette						X		X	
Product Evaluation Scales – Usual Brand			X		X		X	X	
Product Evaluation Scales – Study Cigarette					X		X	X	
Product Evaluation Scales – E-Cigarette							X	X	
Implicit Association Tasks		X		X		X		X	
Perceived Health Risks		X		X		X		X	
Instruct to smoke UB	X								
Receive VLNCC		X		X		X			
Receive e-CLG				X		X			
Flavor Testing†		X							
Support/Troubleshoot				X		X			

\*if call falls on weekend, holiday or other day when the clinic is officially closed, call may be conducted on next business day; \*\*a troubleshooting call may be conducted if reports show at least 2 consecutive days of no EMA data from subject; †procedure waived during COVID-19

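### The planned-cessation exclusion looks 45 days ahead from an unstated start and does not cover Phase 4; the effect on Aim 1 is small, but in exploratory Aim 3 planned quitting cannot be separated from the switch to e-cigs

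*Combined protocol and SAP*

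**What the plan says.** The Table 3 exclusion criteria list "Recent (past 90 days), current, or planned (within the next 45 days) involvement in smoking cessation activities". The text of Human Subjects Involvement, Characteristics and Design gives the same limit: "report recent (past 90 days), current, or planned (within the next 45 days) involvement in smoking cessation activities". Neither place says whether the 45 days run from the telephone screen, the baseline screening (Visit 0) or the randomization visit (Visit 1).

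The last treatment column of Table 4 is "Phase 4 Wks 8-10", with Visit 4 on Day 71. The Study overview sets out the dual-use period: "During phases 3 (weeks 5-7) & 4 (weeks 8-10), smokers will be instructed to freely use any combination of assigned VLNCC and e-cigs". Visit 0 is a visit "which will occur within 30 days of the telephone screen", and a second telephone screen can renew that interval once. Return Visit Schedule and the Visit Window allows up to one month between phases without logging a deviation.

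On the intended population, Specific Aims and the Study overview call participants non-treatment-seeking. The paragraph on the lack of a cessation endpoint says "we only select smokers who are not presently interested in quitting for our electronic cigarette studies for ethical reasons". Table 3 contains no criterion on interest in quitting other than the 45-day rule.

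**The concern.** A smoker who already plans to quit in week 8 or later meets none of the listed exclusions. The protocol says that it does not select people interested in quitting, and gives an ethical reason, but the written criterion does not secure this for the last phase.

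For the analysis, the issue is timing. Planned quitting in the uncovered days falls late in the study, and the late phases are always the dual-use phases. Aim 3 compares usual brand, VLNCC alone and dual use in that fixed order. A fall in CPD caused by a prior plan to quit would be counted with the change that follows the introduction of e-cigs. The plan collects abstinence by timeline follow-back (TLFB) at all contacts, but states no rule for handling a quit attempt in any analysis.

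**Working it through.** **1. Schedule.** The Table 4 day row reads "Study Day -29 1 8 11* 29 32* 50 71 101". Its columns are shifted in the extracted text. I read Day -29 as the phone screen, Day 1 as Visit 0, Days 8, 29, 50 and 71 as Visits 1 to 4, and Days 11 and 32 as the 3-day check-up calls. The phase lengths reproduce this: 1 + 7 × (1 + 3 + 3 + 3) = 71, with phase ends on Days 8, 29, 50 and 71. Phase 3 is Days 29-50 and Phase 4 is Days 50-71.

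**2. Coverage.** Window end = start day + 45. Look-ahead needed = 71 − start day.

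| Count starts at | Window ends | Phase 3 days uncovered | Phase 4 days uncovered | Look-ahead needed to Day 71 |
|---|---|---|---|---|
| Phone screen, Day -29 | Day 16 | 21 of 21 | 21 of 21 | 100 days |
| Visit 0, Day 1 | Day 46 | 4 of 21 | 21 of 21 | 70 days |
| Visit 1, Day 8 | Day 53 | 0 of 21 | 18 of 21 | 63 days |

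No starting point reaches Day 71. Permitted delays between phases move the end of Phase 4 later and widen each gap.

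**3. Inputs for the effect on CPD.** Table 1, daily smokers: VLNC only 14.19; dual use 12.80 at either dose. Ratio = 12.80 / 14.19 = 0.902, which matches the 0.90 in Table 2. The share q of daily smokers who quit as planned is not in the documents, so I assume 2%, 5% and 10%, with 0 CPD throughout Phase 4.

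**4. Aim 1 (ECIG-Hi v ECIG-Lo).** With orders 1:1, half of each dose's observations fall in Phase 4, so both means become 12.80 × (1 − q/2) and their difference stays 0. If the true Hi/Lo ratio were 0.88 (11.264 v 12.80, difference −1.536), the ratio would stay 0.88. The difference would become −1.536 × (1 − q/2): −1.521, −1.498 and −1.459 at 2%, 5% and 10%.

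If 55% had ECIG-Hi first and the model had no period term, the bias in Hi − Lo would be (0.55 − 0.45) × 12.80 × q = 1.28q: 0.03, 0.06 and 0.13 CPD. The Aim 1 analysis text names no period or sequence term.

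**5. Aim 3 (dual use v VLNC only).** Observed ratio = 12.80 × (1 − q/2) / 14.19.

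| Assumed q | Mean dual-use CPD | Ratio to VLNC only | Factor due to quitting |
|---|---|---|---|
| 0 | 12.80 | 0.902 | 1.000 |
| 2% | 12.67 | 0.893 | 0.990 |
| 5% | 12.48 | 0.879 | 0.975 |
| 10% | 12.16 | 0.857 | 0.950 |

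Quitting midway through Phase 4 would halve the shift.

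**6. TNE.** No single direction follows. Table 1 expects log(TNE) in daily smokers to rise from 2.69 on VLNC only to 3.60 with ECIG-Hi. Someone who stops all nicotine would reduce that contrast; someone who stops cigarettes but keeps the e-cig or uses nicotine replacement may not.

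**The case against.** The protocol states its intent more than once: participants are non-treatment-seeking and not presently interested in quitting. A smoker with a fixed quit date would probably not be described that way. The investigator can exclude unsuitable subjects, and the phone-screen appendices, which are not available here, may ask about quit intentions. All this may keep the number of planned quitters low. It does not close the gap, because present interest is not a plan-based criterion with a time limit and Table 3 does not list it.

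It is also true that fixed phase order in Aim 3 confounds any time trend with product. A longer look-ahead removes one source of such a trend, not the design feature.

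A reader might infer three stronger things that the documents do not support:

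- **That planned quitting would be mistaken for a dose effect in the primary contrast.** Dose order is counterbalanced across Phases 3 and 4, so the expected bias is zero when order is balanced. Bias needs an order imbalance without period adjustment, or dropout that differs by order, and the documents give no evidence of either.
- **That at least 25 days of product use are uncovered.** That holds if the count starts at Visit 0. Randomization takes place at Visit 1 once all criteria are met, so a count from Day 8 is possible and leaves 18 days.
- **That a few quitters would create an effect of the detectable size.** At q = 5% the ratio of 0.879 sits close to the 0.88 in Table 2, but most of that distance from 1 is the change already anticipated. Quitting alone contributes a factor of 0.975.

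**Conclusion.** The gap in the criterion is certain on the nominal schedule: 45 days from any screening contact ends before Phase 4 or within its first days, leaving 18 to 21 of its 21 days uncovered. This rests on my reading of the shifted Table 4 columns, which agrees with the phase weeks and the check-up calls.

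The effect on results is modest. Aim 1 gains some noise and, at an assumed 2-10%, loses 1-5% of any absolute CPD difference; the ratio is unchanged and there is no expected bias with balanced order. Aim 3 is exposed, because the CPD ratio would move from 0.902 to between 0.893 and 0.857 under the same assumption, and nothing in the planned analysis separates that from the switch. Aim 3 is exploratory, the share of planned quitters is unknown and may be small, and the direction for TNE is open. I rate this a cheap improvement of minor severity.

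**What to change.** - **Eligibility.** Define the window by event: exclude anyone planning cessation activity before their own Visit 4. Nominally that is 70 days from Visit 0, 100 from the phone screen or 63 from Visit 1, but an event also follows permitted delays, as a day count does not. State the contact at which it is asked, and reconfirm it at Visit 0, or at Visit 1 before randomization. Make the same change in Table 3, the Human Subjects text and the phone screen.
- **Aim 1.** Include a period term in the model.
- **Aim 3.** Pre-specify a sensitivity analysis that flags or excludes participants with quit attempts recorded by TLFB. Keep it as a sensitivity analysis, since some attempts may be prompted by the products themselves. It also covers people already enrolled.

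The cost is a few lines of text and one extra analysis on data already collected. A few smokers with later quit plans become ineligible. The eligibility change helps only future enrollees; the protocol's interim safety summary already counts 176 smokers exposed.

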#### ***Baseline Screening.***

Participants will not be randomized into the study until Visit 1. Participants who remain eligible after the baseline screening visit will be scheduled to return for Phase 1 as soon as the following week after the baseline visit. Participants will be registered in the institutional database (CORe) within 2 business days of signing consent.

At the baseline screening (Visit 0), which will occur within 30 days of the telephone screen, study participants will be asked to provide medical/surgical history (see Appendices E & QQ), smoking history (see Appendix H) and to complete other assessments as shown in Table 4. Additionally, participants will be asked to fill out two forms related to additional contacts should we no longer be able to reach them (see Appendix C). They may also be provided a staff contacts list and an appointment card if eligible during the visit (see Appendices L and NN). Current and past medical history will be collected. These items will be given to a licensed medical professional, such as a research nurse, physician's assistant, or MD, to review eligibility. In some cases, the medical team may request clearance for participation be signed off by the participant's medical provider (see Appendix TT) prior to enrollment.

Participants unable to complete the Baseline screening visit within 30 days of the initial telephone assessment will be allowed to undergo a second telephone assessment and given an additional 30 days to complete the Baseline screening visit. If they do not complete the Baseline by this time point, they will no longer be considered eligible for study participation and must undergo a 90-day waiting period to re-enroll.

#### ***Subject Withdrawal***

A withdrawal occurs when an enrolled subject actively withdraws consent for further participation in the study, prior to completion of the protocol. Subjects may withdraw consent from the trial at any time at their own request, or they may be withdrawn at any time at the discretion of the investigator for safety reasons. All attempts will be made to collect medications, and to conduct all evaluations required by the protocol.

### ***Return Visit Schedule and the Visit Window***

A window will be permissible for all return visits as follows. Ideally, visits 1 to 4 will observe a 7 day window. If the end of the visit window falls on a weekend, holiday, or other day on which the clinic is officially closed, subjects will be allowed to complete the visit during the next business day. If a participant is not able to complete a visit in the preferred window, a maximum window of 1 month between phases will be observed but no deviation will be logged for out of window visits as these are to be expected. A No Show letter may be sent in some cases (see Appendix J). Checkup calls will be conducted around 3 days post Visit 1 and Visit 2 and will have a window of 1 business day. If the call falls on a weekend, holiday, or other day on which the clinic is officially closed, participants will be contacted the next business day. The 30 Day Follow up call will take place ideally between 30 and 45 days after the final clinic visit (or scheduled Visit 4 date), however the end of the window will not close until TLFB data is collected, or the study ends, whichever is sooner. Occasionally, participants ask for a Doctor's Excuse or a Travel Letter, which we may provide at our discretion (see Appendices K and M).

### ***Assessments and Questionnaires***

A study timeline and table of events and assessments are detailed in **Table 4**. Participants that have agreed to electronically receive questionnaires in advance of the visits will automatically be sent an email containing a participant specific link up to 5 days before the scheduled appointment. Participants will have up to 5 days prior to their appointment to access the link and complete the questionnaires. Participants who have not completed the assessments and questionnaires electronically prior to the visit will be asked to complete the assessments and questionnaires during the visit.

**PHQ-9**. Depressive symptoms will be assessed using the PHQ-9 during screening. The PHQ-9 is a multipurpose instrument for screening, diagnosing, monitoring, and measuring the severity of depression. This assessment is brief and useful in clinical practice, as it can be completed by the patient in minutes and be rapidly scored by the study staff. It can also be scored repeatedly, which can reflect improvement or worsening of depression in response to study procedures. Thus, this assessment can be administered at any visit if the participant reports depressive symptoms (see Appendix I).

**GAD-7**. Generalized anxiety will be assessed using the self-administered GAD-7 during the screening session. This assessment has 7 items that can be scored immediately by the study staff. This assessment can also be administered at any visit (see Appendix I).

**ASI-3**. The Anxiety Sensitivity Index will be used to identify whether a patient is experiencing a general sense of worry or has specific concerns relating to symptoms of stress (see Appendix GG).

**K-6**. The Kessler Psychological Distress Scale (K6) is a 5-point Likert scale used as a global measure of distress drawing from depressive and anxiety related symptomology (see Appendix DD).

**Mood History Questionnaire**. The Mood History Questionnaire is a 16-item self-report assessment that will provide information about the participant's mood in their entire life (see Appendix FF).

**CES-D**. The Center for Epidemiologic Studies – Depression Scale (CES-D) is a brief self-report scale designed to measure symptoms associated with depression in the past week. The scale includes 20 items comprising 6 scales reflecting major facets of depression: depressed mood, feelings of guilt and worthlessness, feelings of helplessness and hopelessness, psychomotor retardation, loss of appetite, and sleep disturbance (see Appendix EE).

